17.4.1. LABORATORY SPECIFIC DERIVATIONS

The SI unit conversion and CTCAE grade will be derived through programming.

Document: [REDACTED]

Author: [REDACTED]

Version Number:

2.5

Version Date:

18Feb2022

Template No.: [REDACTED]

Reference: CS_WI_BS005

Effective Date: 02Dec2019

17.4.2. CTCAE GRADING FOR LABORATORY DATA

To identify laboratory values of potential clinical importance, laboratory results will be graded according to NCI CTCAE Ver. 4.03, where applicable ([APPENDIX 6](#)). All grading will be based on laboratory values (being direct or some derived, corrected values) only, regardless of its interventional or symptomatic consequences.

Some modifications to the grading system will be applied:

- Grade 5 refers to fatal outcomes, which cannot be determined solely by laboratory values, therefore will not appear in the grading system.
- A further category denoted Grade 0 would include all laboratory values within normal range except missing values.
- Missing results shall be graded as missing.
- For some specific parameters with CTCAE grading in both high and low direction (e.g., calcium, glucose, magnesium, potassium, sodium), CTCAE in hyper and hypo directions will be presented separately, i.e., hyper for higher values of concern and hypo for lower values of concern.

Any graded abnormality that occurs following the initiation of study drug and represents at least a 1-grade change (i.e. increase or decrease) from the baseline assessment is defined as treatment emergent. The treatment-emergent laboratory abnormality defined by CTCAE will be summarized by CTCAE term, CTCAE toxicity grade, and visit. Any occurrence of grade 3 or grade 4 laboratory abnormality during the treatment period will also be summarized by visit.

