### 1.1 Exclusion Criteria

Patients will be excluded from the study if **any** of the following criteria is met:

1. **Cohort C only:** patients who have been previously been treated with TAS-102 or regorafenib
2. Absolute neutrophil count (ANC)  $< 1.5 \times 10^9/L$ , platelet count  $< 100 \times 10^9/L$ , or hemoglobin  $< 9.0$  g/dL. Blood transfusion within 1 week prior to enrollment for the purpose of increasing the likelihood of eligibility is not allowed;
3. Serum total bilirubin  $> 1.5 \times$  upper limit of normal (ULN);
4. Alanine aminotransferase (ALT) or aspartate aminotransferase (AST)  $> 1.5 \times$  ULN in patients without hepatic metastases; ALT or AST  $> 3 \times$  ULN in patients with hepatic metastases;
5. Serum potassium, calcium, or magnesium levels out of the normal laboratory reference range, and clinically significant in the investigator's judgment;
6. Creatinine  $> 1.5 \times$  ULN or creatinine clearance  $< 60$  mL/min. Creatinine clearance can either be measured in a 24-hour urine collection or estimated by the Cockcroft-Gault equation as follows:  $CrCl$  (mL/min) =  $[(140 - \text{age}) \times (\text{weight in kg}) \div [72 \times (\text{serum creatinine in mg/dL})]]$  (0.85 if female).
7. Urine dipstick protein  $\geq 2+$  or 24-hour urine protein  $\geq 1.0$  g/24-h. Patients with greater than 1+ proteinuria on urinalysis must undergo a 24-hour urine collection;
8. Uncontrolled hypertension, defined as: systolic blood pressure  $\geq 140$  mmHg and/or diastolic blood pressure  $\geq 90$  mmHg;
9. International Normalized Ratio (INR)  $> 1.5$  or activated partial thromboplastin time (aPTT)  $> 1.5 \times$  ULN, unless the patient is currently receiving or intending to receive anticoagulants for prophylactic purposes.
10. Risk of, or active hemorrhage: history or presence of active gastric/duodenal ulcer or ulcerative colitis, active hemorrhage of an unresected gastrointestinal tumor, history of perforation of fistulas; or any other condition that could possibly result in gastrointestinal tract hemorrhage or perforation within 6 months prior to screening
11. History or presence of hemorrhage from any other site (eg, hemoptysis or hematemesis)

within 2 months prior to screening;

12. History of a thromboembolic event (including deep vein thrombosis [DVT], pulmonary embolism, stroke and/or transient ischemic attack) within 6 months prior to screening;
13. Patients with squamous NSCLC;

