14. Clinically significant cardiovascular disease, including but not limited to acute myocardial infarction or coronary artery bypass surgery within 6 months prior to enrollment, severe or unstable angina pectoris, New York Heart Association Class III/IV congestive heart failure, ventricular arrhythmias requiring treatment, or left ventricular ejection fraction (LVEF) <50%;
15. Mean corrected QT interval (QTc) using the Fridericia method (QTcF) >480 msec or any factors that increase the risk of QTc prolongation or risk of arrhythmic events such as hypokalemia, congenital long QT syndrome, family history of long QT syndrome, or unexplained sudden death under 40 years of age in a first-degree relative.
16. Concomitant medications with a known risk of causing QT prolongation and/or torsade de pointes (see list in [Appendix E](#); source list is continuously updated online at [www.qtdrugs.org](http://www.qtdrugs.org));
17. Patients who have ever received a VEGFR inhibitor, **except** for patients with mCRC enrolled in the dose expansion phase;
18. Systemic anti-neoplastic therapies (except for those described in Exclusion 18) or any investigational therapy within 4 weeks prior to the first dose of study drug, including chemotherapy, radical radiotherapy, hormone therapy, biotherapy and immunotherapy;
19. Systemic small molecule targeted therapies (eg, tyrosine kinase inhibitors) within 5 half-lives or 4 weeks (whichever is shorter) prior to the first dose of study drug;
20. Palliative radiotherapy for bone metastasis/lesion within 2 weeks prior to the initiation of study drug;
21. Brachytherapy (ie, implantation of radioactive seeds) within 60 days prior to the first dose of study drug;
22. Use of strong inducers or inhibitors of CYP3A4 within 2 weeks before the first dose of study drug (3 weeks for St John's Wort); P-glycoprotein (P-gp) or breast cancer resistance protein (BCRP) substrate within 2 weeks before the first dose of study drug (see [Appendix F](#) for a list of such medications);
23. Surgery or invasive procedure (ie, procedure that includes a biopsy) within 60 days prior to the first dose of study drug or unhealed surgical incision;
24. Any unresolved toxicities from a previous antitumor treatment greater than

CTCAE v 4.03 Grade 1 (except for alopecia);

25. Known human immunodeficiency virus (HIV) infection;

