## 5.3 Concomitant and Excluded Therapies

### 5.3.1 Concomitant Therapies

Concomitant therapy includes any prescription medications or over-the-counter preparations used by a patient between the 7 days preceding the screening evaluation and the termination visit. All concomitant medications should be reported to the investigator and recorded on the appropriate CRF.

Patients who use hormonal therapy with GnRH agonists for prostate cancer, oral contraceptives, hormone-replacement therapy, or other allowed maintenance therapy should continue their use.

Prophylactic use of anticoagulation for the maintenance of patency of permanent indwelling central venous access devices or for patients at high risk of venous thromboembolism is permitted during study treatment. If patients are receiving anticoagulation, they should be very closely monitored for potential haemorrhage, and:

- Patients who are receiving warfarin or Coumadin-like products should have their INR monitored and maintained at the lower third of the therapeutic range (ie, 2.0-2.3), unless a higher INR is required for anti-thrombotic efficacy.
- Patients who require low-molecular-weight heparin should receive the prophylactic dose and monitoring as specified by the appropriate product information label.

The investigator should closely monitor patients receiving anti-platelet and/or anti-thrombotic drugs with INR, aPTT and platelet count during study drug treatment and make a timely decision on whether to continue or stop such drugs in patients that report Grade  $\geq 2$  haemorrhagic events at any site, based on an individual assessment of the risk-benefit balance (See [Appendix J](#) for additional information on the clinical management of severe or serious haemorrhagic AEs).

Patients that develop arterial thromboembolic events should discontinue the study drug. If a patient suffers a venous thromboembolic event while still receiving study drug, it may still be possible for him or her to remain on study treatment under close monitoring and dose modification of study drug.

All supportive measures consistent with optimal patient care will be given throughout the study.

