### 8.3 Safety Analysis

Safety will be assessed through AEs, laboratory assessments, vital signs, and ECG results. Safety data will be listed and summarized by dose cohort across the 2 phases. All DLT events will be listed by dose cohort for the dose escalation phase only.

Severity of AEs will be graded by the investigator according to NCI CTCAE v4.03. If a CTCAE criterion does not exist, the grade corresponding to the appropriate adjective will be used by the investigator to describe the maximum intensity of the adverse event: Grade 1 (mild), Grade 2 (moderate), Grade 3 (severe), Grade 4 (life threatening), or Grade 5 (fatal) (see Section 7.1.6). All AEs will be coded with Medical Dictionary for Drug Regulatory Activities (MedDRA).

All AEs will be listed. The focus of safety data summarization will be on treatment-emergent adverse events (TEAEs), which are defined as AEs that occur or worsen in the period extending from the first dose of study drug to 30 days after the last dose of study drug in this study.

TEAEs will be summarized as the number of patients and corresponding percentage by MedDRA System Organ Class (SOC) as well as Preferred Term (PT). The incidence of TEAEs, SAEs, adverse events of special interest (AESIs), AEs leading to dose interruption, reduction, or treatment discontinuation will be presented by SOC and PT; by relationship to the investigational product and by toxicity grade for each dose level. Changes in laboratory data will be summarized by severity grade using the NCI CTCAE v4.03. When abnormal laboratory results at the patient level are counted, the worst value during study treatment will be chosen.

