17.2. ADVERSE EVENTS

AEs will be coded using Medical Dictionary for Drug Regulatory Activities (MedDRA) central coding dictionary, Version 23.1 or higher.

Treatment emergent adverse events (TEAEs) are defined as AEs that started or worsened in severity on or after the first dose of study medication and no later than 37 days after the date of last study treatment. In case that the AE onset date coincide with the first dose date of study treatment, AE will be considered as TEAE if the response of question “Did the adverse event occur prior to the start of study treatment?” in AE form is “No”.

See [section 6.3.2](#) for handling of partial dates for AEs. In the case where it is not possible to define an AE as treatment emergent or not, (i.e., the required imputed dates are missing or partial) the AE will be classified by the worst case, i.e. treatment emergent.

An overall summary of number of patients within each of the categories described in the sub-section below, will be provided.

Listings will include all the AEs being reported during the study with flag to distinguish TEAEs and Non-TEAEs. Imputed AE dates will not be presented in the listings.

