APPENDIX 6. CLINICAL LABORATORY PARAMETERS CTCAE CRITERIA

PARAM (SI Unit)	Hypo	Hyper	ATOXGR			
			GRADE 1	GRADE 2	GRADE 3	GRADE 4
		Hemoglobin increased	Increase in >0 - 2 gm/dL above ULN or above baseline if baseline is above ULN	Increase in >2 - 4 gm/dL above ULN or above baseline if baseline is above ULN	Increase in >4 gm/dL above ULN or above baseline if baseline is above ULN	~
Hemoglobin (g/L)	Anemia		Hemoglobin (Hgb) <LLN - 10.0 g/dL; <LLN - 6.2 mmol/L; <LLN - 100 g/L	Hgb <10.0 - 8.0 g/dL; <6.2 - 4.9 mmol/L; <100 - 80g/L	Hgb <8.0 g/dL; <4.9 mmol/L; <80 g/L	~
Platelets (10 ⁹ /L)	Platelet count decreased		<LLN - 75,000/mm ³ ; <LLN - 75.0 x 10e9 /L	<75,000 - 50,000/mm ³ ; <75.0 - 50.0 x 10e9 /L	<50,000 - 25,000/mm ³ ; <50.0 - 25.0 x 10e9 /L	<25,000/mm ³ ; <25.0 x 10e9 /L
Leukocytes (10 ⁹ /L)	White blood cell decreased		<LLN - 3000/mm ³ ; <LLN - 3.0 x 10e9 /L	<3000 - 2000/mm ³ ; <3.0 - 2.0 x 10e9 /L	<2000 - 1000/mm ³ ; <2.0 - 1.0 x 10e9 /L	<1000/mm ³ ; <1.0 x 10e9 /L

Document: [REDACTED]

Author: [REDACTED]

Version Number: 2.5

Version Date: 18Feb2022

Template No.: [REDACTED]

Reference: CS_WI_BS005

Effective Date: 02Dec2019

Neutrophils (10 ⁹ /L)	Neutrophil count decreased		<LLN - 1500/mm ³ ; <LLN - 1.5 x 10 ⁹ /L	<1500 - 1000/mm ³ ; <1.5 - 1.0 x 10 ⁹ /L	<1000 - 500/mm ³ ; <1.0 - 0.5 x 10 ⁹ /L	<500/mm ³ ; <0.5 x 10 ⁹ /L
Lymphocytes (10 ⁹ /L)	Lymphocyte count decreased		<LLN - 800/mm ³ ; <LLN - 0.8 x 10 ⁹ /L	<800 - 500/mm ³ ; <0.8 - 0.5 x 10 ⁹ /L	<500 - 200/mm ³ ; <0.5 - 0.2 x 10 ⁹ /L	<200/mm ³ ; <0.2 x 10 ⁹ /L
		Lymphocyte count increased	~	>4000/mm ³ - 20,000/mm ³	>20,000/mm ³	~
Activated Partial Thromboplastin Time (s)		Activated partial thromboplastin time prolonged	>ULN - 1.5 x ULN	>1.5 - 2.5 x ULN	>2.5 x ULN; bleeding	~
International Normalized Ratio		INR increased	>1.2 - 1.5	>1.5 - 2.5	>2.5	~
Albumin (g/L)	Hypoalbuminemia		<LLN - 3 g/dL; <LLN - 30 g/L	<3 - 2 g/dL; <30 - 20 g/L	<2 g/dL; <20 g/L	~
Glucose (mmol/L)	Hypoglycemia		<LLN - 55 mg/dL; <LLN - 3.0 mmol/L	<55 - 40 mg/dL; <3.0 - 2.2 mmol/L	<40 - 30 mg/dL; <2.2 - 1.7 mmol/L	<30 mg/dL; <1.7 mmol/L
Creatinine (umol/L)		Creatinine increased	>1 - 1.5 x baseline; >ULN - 1.5 x ULN	>1.5 - 3.0 x baseline; >1.5 - 3.0 x ULN	>3.0 baseline; >3.0 - 6.0 x ULN	>6.0 x ULN
Alkaline Phosphatase (IU/L)		Alkaline phosphatase increased	>ULN - 2.5 x ULN	>2.5 - 5.0 x ULN	>5.0 - 20.0 x ULN	>20.0 x ULN

Document: [REDACTED]

Author: [REDACTED]

Version Number:

2.5

Version Date:

18Feb2022

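### SAP 17.4.2 flags a falling laboratory grade as treatment emergent, so a partial improvement can be tabulated as toxicity

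*SAP*

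**What the plan says.** SAP 17.4.2 grades laboratory values by CTCAE v4.03, using the limits in Appendix 6. Values within the normal range are Grade 0. Parameters that can be abnormal in both directions are graded separately as hyper and hypo. A graded abnormality arising after the start of study drug that "represents at least a 1-grade change (i.e. increase or decrease) from the baseline assessment is defined as treatment emergent". The flagged results are then summarized by CTCAE term, grade and visit.

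The same term has a narrower meaning for adverse events. SAP 17.2 defines TEAEs as "AEs that started or worsened in severity on or after the first dose of study medication". In Protocol 8.3 they are "defined as AEs that occur or worsen in the period extending from the first dose of study drug". Neither definition counts an improvement.

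SAP 2.4, which lists changes from the protocol, does not mention the laboratory rule, and nothing else in either document narrows it.

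**The concern.** A CTCAE grade measures severity in one direction, so a lower grade is a better result. Because hyper and hypo are already graded separately, the rule does not need to admit a decrease in order to catch low values. The only effect of the extra words is to admit falling grades.

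A reader of the laboratory table will take treatment emergent to mean new or worse on drug, as it does in the adverse event tables. Some entries would mean the opposite. The study has no control arm in which the same artefact would appear, and the cohorts are small, so a few such entries could change the look of a row.

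**Working it through.** **Step 1. Which grade changes are flagged.** The post-dose value must itself be graded, so it is Grade 1 to 4. Baseline can be Grade 0 to 4. That gives 5 x 4 = 20 cells.

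| Type of change | Cells | As written | Worsening only |
|---|---|---|---|
| Higher grade | 10 | flagged | flagged |
| Lower grade, still abnormal (2→1, 3→1, 3→2, 4→1, 4→2, 4→3) | 6 | flagged | not flagged |
| Same grade | 4 | not flagged | not flagged |
| Total flagged | | 16 of 20 | 10 of 20 |

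A return to Grade 0 is not flagged, because it is no longer an abnormality. The error therefore needs a baseline of Grade 2 or more and a post-dose value that is lower in grade but still abnormal. These are counts of cells, not of patients.

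**Step 2. Whether eligible patients can reach those cells.** The Exclusion Criteria in Protocol Section 4 are compared here with SAP Appendix 6.

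- *Closed by number:* the entry limits for neutrophils, platelets, bilirubin, ALT, AST, creatinine and proteinuria rule out baseline Grade 2 or more.
- *Anemia:* Grade 2 is "Hgb <10.0 - 8.0 g/dL", while exclusion 2 removes only hemoglobin below 9.0 g/dL. A patient at 9.0 to below 10.0 g/dL can enter at Grade 2. A change from 9.5 to 10.5 g/dL is Grade 2 to Grade 1 if the local lower limit of normal is above 10.5 (assumed), and it is flagged.
- *ALP:* no numeric entry limit. A change from 3.0 to 2.0 x ULN is Grade 2 to Grade 1, flagged.
- *Albumin:* no numeric entry limit. A change from 28 to 32 g/L is Grade 2 to Grade 1 if the lower limit of normal is above 32 (assumed), flagged.
- *Triglycerides:* no numeric entry limit. A change from 4.0 to 3.0 mmol/L is Grade 2 to Grade 1, flagged.

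Two exclusions narrow these cases further by judgement. Exclusion 24 bars "Any unresolved toxicities from a previous antitumor treatment greater than" Grade 1, so the anemia case must not be attributed to earlier treatment. Exclusion 33 lets the investigator exclude for a troubling laboratory result.

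**Step 3. INR.** Exclusion 9 sets an INR limit "unless the patient is currently receiving or intending to receive anticoagulants for prophylactic purposes". Protocol 5.3.1 wants warfarin patients "maintained at the lower third of the therapeutic range (ie, 2.0-2.3"), with an exception where a higher value is needed. Appendix 6 grades values above 1.5 and up to 2.5 as Grade 2 "INR increased". A patient held at 2.0-2.3 before and during treatment stays at Grade 2 and is not flagged. A flag needs a grade boundary to be crossed: 2.6 to 2.2 (Grade 3 to 2) or 2.0 to 1.4 (Grade 2 to 1).

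**Step 4. What one miscounted patient is worth.** If the planned cohort size is the denominator (an assumption, since 17.4.2 states none):

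- Cohorts B and C: 1/40 = 2.5 percentage points.
- Cohorts D and E: 1/15 = 6.7 points.
- Cohort A, or one escalation dose level: 1/6 = 16.7 points.

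**Step 5. QTcF (editorial).** SAP 17.5.1 divides QT by the cube root of RR and states no unit, while 17.5 and 17.5.2 list RR in msec. For QT 400 and RR 800 msec:

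- RR in msec: 400 / 800^(1/3) = 43.1.
- RR in seconds: 400 / 0.8^(1/3) = 430.9 msec.

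The ratio is 1000^(1/3) = 10. The limits in 17.5.2 (above 450, 480 and 500 msec) show that seconds are meant.

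**The case against.** The best case on the other side accepts the wording and disputes its weight.

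*Reach.* Entry limits close the error for many parameters. Appendix 6 closes or restricts others: lymphocytes increased has no Grade 1; hypermagnesemia, hypokalemia and hyponatremia have no Grade 2; and hemoglobin increased is graded relative to a raised baseline. A count of terms without an entry limit would therefore overstate exposure to the error. This stands, and no such count is relied on here.

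*INR.* A reader might infer that anticoagulated patients are the main source of false entries, because their target range is itself Grade 2. The documents do not support that. A patient kept in range shows no grade change, so INR is a possible case only.

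*Consequence.* A reader might also infer that laboratory safety reporting as a whole is distorted. It is not. The baseline-to-worst shift tables (17.4), the Grade 3/4 summary (17.4.2) and the liver-injury outputs (17.4.4) do not use the flag, and TEAEs have their own rule. Laboratory findings that meet the criteria in Protocol 7.1.8.4 are still reported as adverse events. No hypothesis is tested, and no efficacy, DLT or dose decision rests on this table.

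*Contradiction.* The protocol does not define a treatment-emergent laboratory abnormality, and the comparison definitions are for adverse events. This is one term used in two senses, not a conflict between the two documents on the laboratory rule.

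*QTcF.* A reader might expect QTcF to be reported tenfold too small. The protocol names the Fridericia method and the msec limits fix the scale, so a literal run would probably be noticed at once. Only a unit note is missing.

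None of this rescues the rule itself. No reading of a fall in grade makes it emergent toxicity.

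**Conclusion.** The point holds in a limited form. As written, SAP 17.4.2 enters partial improvements in the treatment-emergent laboratory table, through 6 of the 16 grade changes that it flags. Eligible patients can show such changes, most plainly in anemia, ALP, albumin and triglycerides.

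The effect is confined to one descriptive table. The number of patients who start at Grade 2 or more and improve without normalizing is not in the documents and may be small. The percentages per patient assume planned cohort sizes as denominators, and the hemoglobin and albumin examples assume the lower limits of normal shown. It should be corrected because the rule gives a wrong result whenever the case arises. The QTcF item is a clarification only.

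**What to change.** In SAP 17.4.2, replace the either-direction condition with: *at least a 1-grade increase (worsening) from the baseline assessment, assessed separately in the hyper and hypo directions*. Check that the program for the treatment-emergent laboratory table applies it.

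In SAP 17.5.1, state QTcF = QT / (RR/1000)^(1/3), with QT and RR in msec.

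Each change costs one line of SAP text and the matching code. No new data are needed.

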17.4.3. LABORATORY REFERENCE RANGES

Quantitative laboratory measurements will be compared with the relevant laboratory reference ranges in SI units and categorized as:

- Low: Below the lower limit of the laboratory reference range
- Normal: Within the laboratory reference range (upper and lower limit included)
- High: Above the upper limit of the laboratory reference range

17.4.4. POTENTIAL DRUG-INDUCED LIVER INJURY (DILI)

Below events will be identified via programming and summarized by categories and dose and/ or disease cohort for the SAS. Separate listings for patients with DILI, as defined below, will also be provided.

Document: [REDACTED]

Author: [REDACTED] Version Number: 2.5
 Version Date: 18Feb2022

Template No.: [REDACTED] Reference: CS_WI_BS005

Effective Date: 02Dec2019

- Hy’s Law: Serum AST or ALT $>3 \times$ ULN and ALP $< 2x$ ULN and total bilirubin $>2 \times$ ULN
- POTENTIAL DRUG-INDUCED LIVER INJURY (DILI): Serum AST or ALT $>3 \times$ ULN and total bilirubin $>2 \times$ ULN
- AST:
 - $> 3x$ ULN and $\leq 5 x$ ULN,
 - $> 5 x$ ULN and $\leq 8 x$ ULN,
 - $> 8 x$ ULN and $\leq 10 x$ ULN,
 - $> 10 x$ ULN and $\leq 20 x$ ULN,
 - $> 20x$ ULN,
 - AST $>5x$ ULN for more than 5 weeks
- ALT:
 - $> 3x$ ULN and $\leq 5 x$ ULN,
 - $> 5 x$ ULN and $\leq 8 x$ ULN,
 - $> 8 x$ ULN and $\leq 10 x$ ULN,
 - $> 10 x$ ULN and $\leq 20 x$ ULN,
 - $> 20x$ ULN,
 - $> 5x$ ULN for more than 5 weeks

Lab abnormalities meeting the biochemical criteria for Hy’s law is associated with a markedly increased possibility of severe DILI. These components will also be listed separately:

- ALP $< 2 x$ ULN
- Total Bilirubin:
 - >1.5 and $\leq 2 x$ ULN
 - $> 2 x$ ULN

17.5. ECG EVALUATIONS

Results of the Electrocardiogram (ECG) will be included in the reporting of this study. Overall assessment of ECG up to 37 days following the date of last dose of study medication will be included for analysis.

The following ECG parameters will be reported for this study:

Document: [REDACTED]

Author: [REDACTED]

Version Number: 2.5

Version Date: 18Feb2022

Template No.: [REDACTED]

Reference: CS_WI_BS005

Effective Date: 02Dec2019

- Heart Rate (bpm)
- PR Interval (msec)
- QT Interval (msec)
- QRS Interval (msec)
- RR Interval (msec)
- QTcF Interval (msec)

Overall assessment of ECG (Investigator’s judgment): Normal, NCS, CS.

The following summaries will be provided for ECG data:

- Observed and change from baseline by visit
- Markedly abnormal value and change of ECG by visit
- Shift table of change from baseline to worst post-baseline ECG assessment by investigator

Listing of ECG data (Assessment date, Timepoint, HR, PR interval, QT interval, QRS interval, RR interval, QTcF interval) by patients, with results which meet the markedly abnormal criteria being flagged.

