5.3. UNSCHEDULED VISITS AND EARLY TERMINATION DATA

In general, for by-visit summaries, data recorded at the nominal visit will be presented. Unscheduled measurements will not be included in by-visit summaries, but will contribute to the best/ worst case value where required (e.g., shift table).

Listings will include scheduled, unscheduled, and early discontinuation data.

Document: [REDACTED]

Author: [REDACTED]

Version Number:

2.5

Version Date:

18Feb2022

Template No.: [REDACTED]

Reference: CS_WI_BS005

Effective Date: 02Dec2019

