5.4. WINDOWING CONVENTIONS

The visit-window mapping is described in [APPENDIX 4](#). Visit-based summaries will be based on the windowed visits. All data, whether or not within the visit windows, will be presented in listings.

For windowed visits during the treatment cycles,

- If more than 1 assessment occurs during a visit window, the assessment closest to the scheduled day will be assigned to the windowed visit.
- If two assessments are equidistant from the scheduled day, the later assessment will be assigned to the windowed visit.
- If there are multiple assessments on the same day, the worst case will be used.

For the post-treatment visit, the last assessment in the window will be included in the summary. The window for the post-treatment visit will be "from the last dose date + 8 days to the last dose date + 37 days".

For a patient who prematurely discontinues the study, the premature visit will be slotted accordingly.

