7. OUTPUT PRESENTATIONS

[Appendix 2](#) shows conventions for presentation of data in outputs.

Format and content of summary tables, figures, and listings are presented as mock shells for TFLs and provided by IQVIA Biostatistics.

Continuous variables will be summarized using descriptive statistics including, number of patients (n), mean, median, standard deviation (STD), 25% and 75% quantiles, minimum and maximum. Categorical variables will be summarized with number and percentage and presented in frequency tables. All results will be presented by dose cohort (only in dose escalation phase) or tumor specific cohorts (only in dose expansion phase).

Qualitative variables will be summarized by count(s) and percentages (%).

Percentages will be reported with 1 decimal point; if the count is 0, no percentage will be presented. Value of percentage less than 1% will be presented as “<1%.” Value of percentage less than 100% but >99% will be presented as “>99%.” Any rounding will be done after all calculations are made.

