17.5.2. MARKEDLY ABNORMAL CRITERIA

Markedly abnormal criteria for ECG are listed in table below:

Parameter (unit)	Criterion value
Heart Rate (bpm)	>120
	<50
PR Interval (msec)	≥ 210
RR Interval (msec)	> 1200
	< 500
QRS Interval (msec)	≥ 120
	≤ 50
QT Interval (msec)	≥ 500
	≤ 300
QTcF (msec)	> 450

Document: [REDACTED]

Author: [REDACTED]

Version Number: 2.5

Version Date: 18Feb2022

Template No.: [REDACTED]

Reference: CS_WI_BS005

Effective Date: 02Dec2019

	> 480
	> 500
	≤ 300
	Increase from baseline > 30
	Increase from baseline > 60
	Decrease from baseline > 30
	Decrease from baseline > 60
	> 450 and increase from baseline > 30
	> 500 and increase from baseline > 60

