17.6. VITAL SIGNS

The following Vital Signs measurements performed within 37 days after the date of last dose of study medication will be reported for this study:

- Heart rate (bpm)
- Respiratory rate (bpm)
- Body Temperature (C)
- Weight (kg)
- Systolic blood pressure (mmHg)
- Diastolic blood pressure (mmHg)

The following summaries will be provided for vital signs data:

- Observed and change from baseline by visit
- The frequency and percentage of patients with any potentially clinically significant findings defined in section 17.6.2 during the treatment period will be presented.

Listing of vital sign data will also be generated.

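### SAP 17.5 summarizes the markedly abnormal ECG criteria by visit only, so the SAP text plans no count of patients who ever crossed a QTcF threshold

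*SAP*

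**What the plan says.** SAP 17.5 plans three ECG summaries: observed values and changes at each visit; "Markedly abnormal value and change of ECG by visit"; and "Shift table of change from baseline to worst post-baseline ECG assessment by investigator". The investigator's rating in the third has three levels: normal, abnormal but not clinically significant, and abnormal and clinically significant. A by-patient listing flags results that meet the criteria.

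The criteria are in SAP 17.5.2. They cover heart rate, PR, RR, QRS, QT and QTcF, and run up to combined limits such as "> 500 and increase from baseline > 60".

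On unscheduled data, SAP 5.3 says: "Unscheduled measurements will not be included in by-visit summaries, but will contribute to the best/ worst case value where required (e.g., shift table". Listings do include unscheduled data. On windows, SAP 5.4 says: "If more than 1 assessment occurs during a visit window, the assessment closest to the scheduled day will be assigned to the windowed visit". The worst value is taken only among ECGs on the same day, and the last ECG is taken for the post-treatment visit.

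Two neighbouring sections count by patient. For vital signs, SAP 17.6 says: "The frequency and percentage of patients with any potentially clinically significant findings defined in section 17.6.2 during the treatment period will be presented". For liver thresholds, SAP 17.4.4 says: "Below events will be identified via programming and summarized by categories and dose and/ or disease cohort for the SAS". For laboratory data, SAP 17.4 uses scheduled and unscheduled assessments to find the worst post-baseline value.

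**The concern.** The usual question of a QTcF outlier table is how many patients ever went above 480 or 500 msec, or rose by more than 60 msec. A table with one row per visit does not answer it. The same patient may appear in several rows, and a patient who crossed only between scheduled visits appears in none.

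The protocol gives the question some weight. Exclusion criterion 15 keeps out patients with QTcF above 480 msec, and drugs with a known QT risk are prohibited. Protocol 6.3.4 asks for close monitoring of QTcF and for additional cardiac tests as clinically indicated. An ECG done because something looked wrong is likely to be unscheduled, and so is the kind left out of the by-visit rows.

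Adverse event tables do not fill the gap. They depend on the investigator reporting the event. Protocol 7.1.8.4 sets reporting criteria for laboratory values and vital signs without naming ECG values, and QT prolongation is not among the ten categories of special interest in SAP 17.2.6.

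**Working it through.** The plan states no figure to reproduce. The check is to trace where a QTcF threshold crossing would be counted.

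**Criteria concerned (SAP 17.5.2).** Heart rate 2 + PR 1 + RR 2 + QRS 2 + QT 2 + QTcF 10 = 19.

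**Where each output stands.**

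| Planned output | Uses the 17.5.2 limits? | Unscheduled ECGs? | Gives patients who ever crossed? |
|---|---|---|---|
| Observed and change by visit (17.5) | No | No (5.3) | No |
| Markedly abnormal by visit (17.5) | Yes | No (5.3) | No, one count per visit |
| Worst-rating shift table (17.5) | No, investigator's rating | Yes (5.3) | No, counts ratings |
| Flagged listing (17.5) | Yes | Yes (5.3) | Only by hand count |
| Adverse event tables (17.2.1) | No | Only if reported | No, counts reported events |

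Only the second and fourth outputs use the limits. One is by visit and the other is a listing.

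**Can the by-visit rows be combined?** For one criterion in a cohort of N patients, let r be the count in each visit row. Let R be the number of patients who crossed on an ECG kept in some row. Then

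largest r ≤ R ≤ the smaller of N and the sum of the r.

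For example, two rows showing 1 patient each are consistent with R = 1 or R = 2. The number who ever crossed is E = R + U, where U counts patients who crossed only on an ECG that no row keeps. So no single row can exceed E, and each may fall short of it. The sum of the rows may be above E (repeat crossings) or below it (if U is large). Nothing in the documents gives U.

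**Does windowing bring unscheduled ECGs back in?** Suppose SAP 5.4 is read as admitting them, despite SAP 5.3. Appendix 4 then gives these ECG windows: Cycle 1 Day 1; Cycle 1 Day 2 to three days before cycle end; Day -3 to Day 3 of each later cycle; and post-treatment.

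- In Cycle 1, take assumed values of 510 msec on an unscheduled Day 10 ECG and 455 msec on the scheduled Day 15 ECG. Both fall in the second window. Distances from Day 15 are 5 days and 0 days, so the 455 is kept and the 510 is not counted.
- From Cycle 2 on, a mid-cycle ECG falls in no ECG window and is not counted.
- After treatment, the last ECG is kept, whether or not it is the worst.

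Under either reading, the retained value need not be the patient's worst.

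**Precedents within the SAP.** SAP 17.6 gives a per-patient count of any finding, but limits it to the treatment period and does not mention unscheduled measurements. The precedent for using unscheduled values is the laboratory worst-value rule in SAP 17.4. SAP 17.4.2 also summarizes grade 3 or 4 laboratory abnormalities by visit, but SAP 17.4 sets a worst-grade shift table beside that summary. The QTcF limits have no such companion.

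**The case against.** The strongest objection is that table content lies elsewhere. SAP 7 says: "Format and content of summary tables, figures, and listings are presented as mock shells for TFLs". The shells were not available for this review, and the ECG table may already carry a row for any post-baseline crossing. That stands, and it limits the point to the SAP text.

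Second, the information is not lost. The listing holds every ECG with flags, and in cohorts planned at 6 to 40 patients a hand count is feasible. That also stands, although a listing is not a planned summary.

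Third, by-visit threshold summaries are a convention of this SAP and not peculiar to ECG, as SAP 17.4.2 shows. This is right as far as it goes. A reader might infer that ECG was singled out for weaker reporting, and the documents do not support that. The difference is only that laboratory data also have a worst-case table on the numeric scale.

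Fourth, the words by visit in the ECG bullet could be read as applying to change alone. The preceding bullet already covers change by visit, so that reading is less natural. At best the text is ambiguous, and the same sentence would settle it.

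Two further inferences go too far. One is that the protocol is breached: Protocol 8.3 asks for the patient's worst value for laboratory results only and requires no ECG threshold count. The other is that the concentration-QT evaluation is harmed: SAP 1 places PK and pharmacodynamic analyses outside this document, and threshold counts are not that analysis.

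**Conclusion.** The point holds for the SAP text. Followed as written, the threshold table misses a patient whose only QTcF crossing is on an unscheduled or off-window ECG, and it cannot give the number of patients who ever crossed any of the 19 limits.

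The size is unknown. The documents give no expected number of unscheduled ECGs and no expected frequency of QTcF outliers, so no percentage can be attached. A reader might infer that QT prolongation would be hidden or substantially under-reported. The documents do not show that: flagged listings, the investigator-rated shift table and reported adverse events all remain, and QT prolongation is not among the identified risks in Protocol Table 3.

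No hypothesis test, primary endpoint or dose decision is affected. This is a low-severity improvement to safety reporting. It rests on the assumption that the mock shells add nothing to the text on this point.

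**What to change.** In SAP 17.5, add for each criterion in 17.5.2 the number and percentage of patients meeting it at any post-baseline ECG, scheduled or unscheduled, up to 37 days after last dose. That cut-off is the one SAP 17.5 already uses for ECG data. Keep the by-visit table as supportive. If the shells already contain this row, one confirming sentence in SAP 17.5 is enough.

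The cost is that sentence and one extra table row per criterion: 19 rows, of which 10 are for QTcF. No new data are needed, since the ECGs are already collected and listed. If the tables have already been produced, the rows can go in a supplementary table.
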